INVESTIGATOR NAME (PRINT): _____

INITIAL/DATE:

INVESTIGATOR SIGNATURE: _____

Stamp Date Received: _____

Receipt _____

DATE: / /
 D D M M M Y Y Y Y

For Stryker Use Only

Entry _____

Verification _____

Monitored _____

[name]

SUBJECT ID: **6 8**
 Study # Site # Subject #**GENERAL INFORMATION**SUBJECT INITIALS:
(If there is no middle initial please use "-") ONSET DATE: / /
 D D M M M Y Y Y Y**III. TREATMENT** Yes* No

* If Yes, specify below

REVISIONS / REMOVALS: (Check all that apply)

- Acetabular Shell
- Acetabular Insert
- Femoral Bearing Head
- Modular Neck / Modular Stem (Complete Study Termination form)
- Other

For Stryker Implants, submit PER form and implant(s) to Stryker.

Date of Treatment

 /  / 
 /  / 
 /  / 
 /  / 
 /  / 
D D M M M Y Y Y Y

RE-OPERATIONS: (Specify)

-
-

 /  / 
 /  / 
D D M M M Y Y Y Y

OTHER TREATMENTS: (Specify)**ANESTHESIA USED?** Yes No

-
-
-
-
-

 /  / 
 /  / 
 /  / 
 /  / 
 /  / 
D D M M M Y Y Y Y

RESOLUTION OF EVENT:

- Unresolved as of
- Resolved as of

* Submit copy of this form when event resolved.

 /  / 
 /  / 
D D M M M Y Y Y Y

*

IV. COMMENTS**INVESTIGATOR NAME (PRINT):** **For Stryker Use Only**

INITIAL/DATE:

Receipt _____

INVESTIGATOR SIGNATURE:

Stamp Date Received:

Entry _____

DATE: / /
 D D M M M Y Y Y Y

PER#.

Verification _____

Monitored _____

SUBJECT ID:

6 8

Study #

Site #

Subject #

GENERAL INFORMATION

SUBJECT INITIALS:

--	--	--

(If there is no middle initial please use " - ")

OPERATIVE SIDE: (use one form per side)

 Right Left

DATE OF

DEVIATION:

--	--

D D

--	--	--

M M M

--	--	--

Y Y Y

--	--	--

Y Y Y

I. DEVIATION INFORMATION

(Report One Deviation per form)

A. TYPE OF DEVIATION (Check one)

 Informed Consent: (Check one)

- Study procedures performed prior to informed consent
- Incorrect informed consent version used
- Other (Specify) _____

 Inclusion / Exclusion: Subject enrolled does not meet the inclusion / exclusion criteria **Treatment:** Protocol specified study component(s) not implanted (Check all that apply)

 Acetabular Shell	 Acetabular Insert	 Femoral Bearing Head
 Modular Neck / Modular Stem*	 Other (Specify) _____	

*(Complete Study Termination form)

 Evaluation(s): (Specify one visit below)

VISIT: Pre-Op 6 Week 1 Year 2 Year 3 Year 4 Year 5 Year 6 Year 7 Year 8 Year 9 Year 10 Year

(Specify one selection)

- Missed entire visit
- Deviation in visit (Check all that apply and specify)
 - Required form(s)/X-ray(s) not done
 - Evaluation(s) occurred outside of protocol specified time window
 - X-ray Unevaluable (i.e. unreadable/poor quality)

(If Deviation in visit, specify each form/X-ray)

- Biomechanical Measurement
- Follow-up Questionnaire
- Functional Evaluation
- SF-12
- LEAS
- X-ray - A/P Pelvis
- X-ray - A/P Femur
- X-ray - Lateral

 Other: (Specify) _____

B. Briefly describe the deviation and why this occurred. _____

INVESTIGATOR NAME (PRINT):

INVESTIGATOR SIGNATURE:

DATE:

--	--

 /

--	--	--

 /

--	--	--

D D M M M Y Y Y Y

Stamp Date Received:

INITIAL/DATE:

Receipt _____

Entry _____

Verification _____

Monitored _____

For Stryker Use Only

[name]

SUBJECT ID: **6 8**
 Study # Site # Subject #**GENERAL INFORMATION**SUBJECT INITIALS:
(If there is no middle initial please use "-")OPERATIVE SIDE: (use one form per side)
 Right LeftTERMINATION DATE: / /
D D M M M Y Y Y Y**I. STUDY TERMINATION****A. DID SUBJECT COMPLETE STUDY ACCORDING TO PROTOCOL?** Yes No*

* If No, answer questions B and C

B. CHECK ONE PRIMARY REASON BELOW:

- Death (Complete AE form)
- Investigative Site Terminated
- Lost To Follow-Up

List efforts to contact subject:

1st phone call:

	

	

	

2nd phone call:

3rd phone call:

Certified letter sent:

Additional efforts:

- Revision/Removal of Study Device (Complete AE form)
- Study Device Not Implanted (Specify, complete Protocol Deviation form)

- Subject Withdrawal

C. WAS STUDY DEVICE IN PLACE AT DATE OF LAST CONTACT? Yes No**II. COMMENTS**

INVESTIGATOR NAME (PRINT):

INVESTIGATOR SIGNATURE:

DATE: / /
D D M M M Y Y Y Y

Stamp Date Received:

For Stryker Use Only

INITIAL/DATE:
Receipt _____
Entry _____
Verification _____
Monitored _____

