Such events will not be captured on the AE CRF but rather will be captured on the postoperative functional evaluation at the 6-week, 1-year, 2-year, 3-year, 4-year and 5-year time points (as well as at optional 7 and 10-year visits). On these functional evaluations, investigators and SCs will be prompted to question subjects as to whether they have seen a doctor for any reason, been hospitalized for any reason or have a current impediment to their function.

The following decision tree facilitates identification of AEs for which reporting is required under this study protocol:

CONFIDENTIAL

Figure 1
Adverse Event Decision Tree

CONFIDENTIAL

General Physical Examination Findings

At screening for inclusion into the study, any clinically significant abnormality should be recorded as a preexisting condition and reported on the Demographics CRF. From the time of consent forward, any new clinically significant findings or abnormalities that meet the definition of a protocol defined AE must also be recorded and documented as an AE.

Adverse Event Reporting Period

The study period during which AEs must be reported is normally defined as the period from the initiation of any study procedures to the end of the study treatment follow-up. The start of study procedures is considered to be the point of consent. Any AEs which fit the protocol defined reportable events must be reported from the time of consent until study completion.

At each contact with the subject the investigator must seek information on AEs by specific questioning and, as appropriate, by examination. Information on protocol defined AEs should be recorded immediately in the source document and also in the appropriate AE module of the CRF. All clearly related signs, symptoms and abnormal diagnostic procedure results should be recorded in the source document and grouped under one diagnosis as appropriate. The clinical course of each event should be followed until resolution or until it is determined at the end of the study that the AE will not resolve.

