8.2 General Adverse Event Definitions

Following is a list of general AE definitions. For the purposes of this study, only SAEs, excluding elective procedures, as well as all AEs related to the operative site should be reported.

Adverse Event

An **AE** is any untoward medical occurrence in a clinical investigation subject, which changes the medical baseline of the subject. An AE can be an unfavorable and unintended sign, symptom or disease, whether or not related to the study device (AEs may also be referred to as complications). See Section 8.1, Reporting of Adverse Events, for the AE reporting requirements for this study.

CONFIDENTIAL

Anticipated Adverse Event

An **anticipated AE** is an AE, of which the nature, severity or degree of incidence is known and identified in applicable product labeling, published literature or study protocol. The list of anticipated events is provided in Section 12, Risk/Benefit Assessment.

Serious Adverse Event

A **SAE** meets one or more of the following definitions:

- Resulted in in-patient hospitalization
- Resulted in prolonged existing hospitalization
- Resulted in persistent or significant disability/incapacity
- Resulted in permanent impairment of a body function or permanent damage to a body structure
- Necessitated medical or surgical intervention to preclude permanent impairment of a body function or permanent damage to a body structure
- Was a life-threatening situation
- Resulted in patient death

Elective procedures meeting the definition of an SAE do not need to be reported as AEs according to this study protocol.

Adverse Device Effect

An **adverse device effect** (ADE) is a negative change in the subject's health that may have been caused by, or associated with, the use of the device.

Unanticipated Adverse Device Effect

An **unanticipated adverse device effect** (UADE) is any serious adverse effect on health, safety or any life-threatening problem or death caused by, or associated with, a device if that effect is a problem or death not previously identified in nature, severity or degree of incidence, or any other unanticipated serious problem associated with a device and related to the rights, safety or welfare of subjects.

CONFIDENTIAL

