- Normally without using a rail
- Normally using a railing
- In any manner
- Unable to use stairs

F. SOCKS / SHOES (Check One)

- With ease
- With difficulty
- Unable

G. SITTING (Check One)

- Any chair, 1 hour
- High chair, 1/2 hour
- Unable to sit comfortably in any chair

H. PUBLIC TRANSPORTATION

- Able to use
- Not able to use

I. ABSENCE OF DEFORMITY (Operative side only)

Yes No

Yes No

Fixed flexion contracture < 30°

Fixed internal rotation in extension < 10°

Fixed adduction < 10°

Leg length discrepancy < 3.2 cm

 (Specify) . cm**K. RANGE OF MOTION** (Operative side only)

Permanent (Fixed) Flexion

 °

Adduction to

 °

Flexion to

 °

External Rotation in Extension to

 °

Abduction to

 °

Internal Rotation in Extension to

 °**J. THIGH PAIN** (Operative side only)Present at current visit: Yes* No

*If Yes, complete the following:

Describe History or Causative Event:

Is the Thigh Pain Distal?

 Yes No

Is the Thigh Pain Activity Limiting?

 Yes No

Is the Thigh Pain Constant?

 Yes No

What is the subject's perception of the Thigh Pain level on a One to Ten (1-10) scale?: (Check One)

Very slight pain Worst Pain
1 2 3 4 5 6 7 8 9 10

[name]

SUBJECT ID: **6 8**
Study # Site # Subject #**GENERAL INFORMATION**SUBJECT INITIALS:
(If there is no middle initial please use "-") VISIT: 6 Week 1 Year 2 Year 3 Year 4 Year 5 Year 7 Year 10 Year**IV. EVENTS**L. Have there been any protocol defined Adverse Events since the last visit? Yes* No

*If Yes, complete an AE form for each.

USE THIS SECTION TO REPORT MEDICAL EVENTS OTHER THAN PROTOCOL DEFINED ADVERSE EVENTS.M. Has the subject seen a doctor for any medical event since the last visit? Yes* No

*If Yes, specify:

N. Has the subject been hospitalized for any elective surgery since the last visit? Yes* No

*If Yes, specify and check all that apply:

 Contralateral Hip Contralateral Knee Ipsilateral Knee Contralateral Shoulder
 Ipsilateral Shoulder Cataract Other (Specify)

*Provide details:

O. Is anything currently affecting the subject's function? Yes* No

*If Yes, specify:

V. COMMENTS

INVESTIGATOR NAME (PRINT):

INVESTIGATOR SIGNATURE:

DATE: / /
 D D M M M Y Y Y YINITIAL/DATE:
Stamp Date Received:
Receipt
Entry
Verification
Monitored
For Stryker Use Only

[name]

SUBJECT ID: **6 8**
Study # Site # Subject #**GENERAL INFORMATION**SUBJECT INITIALS:
(If there is no middle initial please use "-") VISIT DATE: / / / / / / /

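### The follow-up form asks about hospitalization only for elective surgery, although section 8.1 promises a question about hospitalization for any reason

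*Combined protocol and SAP*

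**What the plan says.** Section 8.1 (Reporting of Adverse Events) makes two classes of event reportable: serious AEs other than elective procedures, and all operative-site AEs. Of the exempt elective procedures it says "Such events will not be captured on the AE CRF but rather will be captured on the postoperative functional evaluation". It then says that this form will prompt investigators and coordinators to ask subjects "whether they have seen a doctor for any reason, been hospitalized for any reason or have a current impediment to their function".

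Section 8.2 lists the seriousness criteria. The first is "Resulted in in-patient hospitalization".

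In Appendix F, part IV (Events) of the postoperative functional evaluation form has four items:

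- Item L: "Have there been any protocol defined Adverse Events since the last visit". A Yes requires an AE form for each event.
- A heading over the remaining items: "USE THIS SECTION TO REPORT MEDICAL EVENTS OTHER THAN PROTOCOL DEFINED ADVERSE EVENTS".
- Item M: "Has the subject seen a doctor for any medical event since the last visit". A Yes asks for a free-text specification.
- Item N: "Has the subject been hospitalized for any elective surgery since the last visit". A Yes leads to tick boxes for other joints, cataract and other.
- Item O: whether anything is currently affecting function.

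The form is completed at six required visits (6 weeks and years 1 to 5) and at the optional visits at years 7 and 10. Section 11.1 describes the case report forms as drafts. Section 11.4 calls them the main instrument for data collection and refers to a completion guide issued separately.

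**The concern.** The protocol describes an open screening question, and the form replaces it with one confined to admissions that need not be reported. An unplanned admission for an untoward event is the typical serious AE, and the form has no plain question for it. An orthopaedic centre may not hear of a medical admission elsewhere unless it asks.

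What is at stake is how completely serious AEs are ascertained. Section 2.2 plans to compare them with the historical control and with published data, and section 9.2.2 plans AE rates with 95% confidence intervals and, if appropriate, a Fisher's exact test between groups. An event that is never elicited enters none of these.

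**Working it through.** The plan gives no figure to reproduce and no arithmetic applies. The check is a comparison of texts.

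**Step 1. Match the prompts.** Section 8.1 names three questions, and the form carries three items in the same order.

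| Topic | Section 8.1 | Appendix F form |
|---|---|---|
| Doctor contact | any reason | Item M: any medical event |
| Hospitalization | any reason | Item N: elective surgery only |
| Function | current impediment | Item O: anything now affecting function |

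The first and third rows agree in substance. The second does not. The shared order shows that item N is the form's version of the promised hospitalization question.

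**Step 2. Decide which admissions are reportable.** By section 8.2, an untoward event that leads to in-patient admission is serious. By section 8.1, a serious event is reportable unless it is an elective procedure. Reportable admissions are therefore the non-elective ones, which item N does not ask about.

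**Step 3. Follow one case through the form.** Suppose a subject had an unplanned medical admission at another hospital between two annual visits.

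- Item N: the correct answer is No.
- Item L: the answer is Yes only if staff know of the admission and have recognised it as a protocol defined AE. The item records a classification already made.
- Item M: the subject has presumably seen a doctor, so a Yes is likely. The follow-up is free text with no instruction to complete an AE form, and the heading reserves the item for events that are not protocol defined AEs.
- Item O: positive only if the event still affects function.
- Outside the form: section 8.1 requires the investigator to question the subject specifically about AEs at every contact.

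The admission can be found, but by inference and not by a direct question.

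**Step 4. Look for another form that asks.** The questionnaire for years 6 to 10 covers hip pain, satisfaction and surgery on the study hip. It has no hospitalization question, although section 8.1 keeps AE reporting open until study completion. Section 8.1 does not promise the prompt on that questionnaire, so this is no second contradiction; it only means the gap is not filled there.

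**The case against.** The best defence is that item N does the job its position gives it. The sentence in section 8.1 follows directly on the account of how exempt elective procedures are captured, and item N sits under a heading for events that are not protocol defined AEs. Reportable events have their own item, L, which comes first, is asked at every visit and triggers an AE form. Item M is broad. Specific questioning is required at each contact, section 8.4 requires events between visits to be recorded, and section 13.1 has monitors compare source documents with the forms at least once a year. The forms are drafts, and the separate completion guide may clarify the item.

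Much of this stands. A reader might infer from item N that the form finds the exempt admissions and misses the reportable ones. The documents do not support that: item N alone does not ask about them, but item L, item M and the questioning duty all remain.

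The defence does not remove the mismatch. Section 8.1 extends the question to any reason for admission, even in its elective-procedure context, and the form does not ask it. The other routes rely on recognition, free text or unscripted questioning. Draft status makes correction easier; it does not make the two texts agree.

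**Conclusion.** The contradiction between section 8.1 and item N is certain from the text. Its consequence is a possible under-ascertainment of serious AEs that involve unplanned admission. How large this is depends on how often items L and M, specific questioning and monitoring fail to bring out an admission, and the documents give nothing to estimate that. The point merits correction but does not threaten the main conclusion of the study.

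Three further inferences are tempting and should not be drawn.

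- *That only the Rejuvenate rate is lowered.* The control study's form is not in the documents, so its questions cannot be compared. The note to Table 4 says the Trident X3 protocol also required operative-site AEs and serious events. A differential bias is possible but not shown.
- *That Table 4 gives the size.* Its Stryker-study rates for cardiovascular, genitourinary and gastrointestinal events (4.89%, 3.23% and 2.15%) are not admission rates. They pool seven studies, some of which required all AEs to be reported. Missed admissions would not reduce such rates in a known proportion.
- *That the primary endpoint suffers.* Stem/neck revision or removal is an operative-site event, reportable whatever its seriousness, and section 10.3 makes it a failure and a study termination. No effect on it is demonstrated.

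**What to change.** Reword item N to read: *Has the subject been hospitalized for any reason since the last visit?* Give it two branches: *elective procedure (specify)*, and *other: assess against the protocol AE definition and, if met, complete an AE form*. The first branch keeps the present tick boxes and uses the exemption as section 8.1 words it, for procedures and not only surgery. The second asks for an assessment and does not demand an AE form for every remaining admission, so events outside the reporting definition are not forced onto AE forms.

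Amend the heading above items M to O so that it no longer limits them to events other than protocol defined AEs. Otherwise the second branch would contradict it. Check the separate completion guide for the same wording.

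The cost is a small revision to one draft form and a few more events for staff to classify. No endpoint, reporting rule or analysis changes.
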